Finally, there are sparse data regarding reactogenicity of COVID-19 vaccine when co-administered with other recommended vaccines. In all of the pediatric Phase III clinical trials to date, receipt of any vaccine within 7 days of enrollment was an exclusion criterion (8). The current CDC clinical considerations for COVID-19 vaccine do allow for receipt of COVID-19 vaccines on the same day as other vaccines. The guidance states that if multiple vaccines are administered at a single visit, each should be administered at a different injection site. (9). However, published data regarding the safety and reactogenicity of this approach are lacking.

In September 2022, the FDA amended the use of the Pfizer-BioNTech vaccine to authorize bivalent vaccine for individuals ≥ 12 year-old (10). However, there are no clinical data regarding the safety and immunogenicity of the BA.4 and BA.5 variant vaccines currently available in the United States.

Herein, we propose a prospective observational safety study of children receiving COVID-19 vaccine per standard of care, including booster doses. We hope to fill existing knowledge gaps concerning the safety of COVID-19 vaccines in the pediatric population by including children who were excluded from the trials, such as adolescents with a prior history of COVID-19 and those receiving concomitant vaccines. We also plan to make every effort to recruit a racially and ethnically diverse pediatric population.

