2 STUDY OBJECTIVES

Primary Objective (PO):

To characterize the safety of authorized and recommended COVID-19 vaccines among children and adolescent participants

Secondary Objective (SO):

To assess the safety of simultaneous administration of COVID-19 vaccine with other routinely recommended vaccines among children and adolescent participants

Exploratory Objectives (EO):

EO 1: To assess adolescent and parent perceptions of the COVID-19 vaccine recommendations and experience with receipt of the vaccine

EO 2: To assess the safety of COVID-19 vaccine stratified by baseline COVID-19 serostatus (positive versus negative) in a subset of child and adolescent participants

EO 3: To assess adverse events of special interest through 6 months after dose 2 of COVID-19 vaccine or a booster dose

EO 4: To assess serious adverse events through 6 months after dose 2 of COVID-19 vaccine or a booster dose

EO 5: To assess immune responses to SARS-CoV-2 antigens after COVID-19 vaccine

Primary Outcome Measures (POM):

POM 1: Proportion of participants with defined local or systemic reactogenicity events (stratified according to severity and in total) on days 1-7 after each dose of COVID-19 vaccine

POM 2: Proportion of participants with at least one severe (Grade 3) solicited local or systemic reactogenicity event on days 1-7 after each dose of COVID-19 vaccine

POM 3: Proportion of participants with at least one moderate-to-severe (Grade 2-3) solicited local or systemic reactogenicity event on days 1-7 after each dose of COVID-19 vaccine

POM 4: Proportion of participants with an unsolicited adverse event on days 1-7 after each dose of COVID-19 vaccine

POM 5: Proportion of participants with an adverse event of special interest through 29 days after dose 2 of COVID-19 vaccine or a booster dose

POM 6: Proportion of participants with at least one serious adverse event occurring through 29 days after dose 2 of COVID-19 vaccine or a booster dose and a description of the serious adverse events

Secondary Outcome Measure (SOM):

SOM: Assessment of primary outcome measures 1-6 in those receiving other routinely recommended vaccines simultaneously with each dose COVID-19 vaccine versus those receiving COVID-19 vaccine alone

Exploratory Outcome Measures (EOM):

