5.5 Reactogenicity & Safety Assessment

Frequency and occurrence of local and systemic reactogenicity events will be assessed through post-vaccination Day 7 using a standard memory aid. At the time of study enrollment, participants will be given a thermometer and instructed on using the memory aid to document oral temperatures and post-injection symptoms. Beginning on the evening following the first COVID-19 vaccination, LARs/participants will record the participants oral temperature using the study-supplied thermometer, the occurrence of solicited and unsolicited AEs, and concomitant medication use for the next 7 days (Day 1 – 7). Similarly, following the second COVID-19 vaccination, LARs/participants will record the participant's oral temperature using the study-supplied thermometer, the occurrence of solicited and unsolicited AEs, and concomitant medication use for the next 7 days. Temperature will be recorded at roughly the same time each day. If a temperature $> 100^{\circ}\text{F}$ (37.8°C) is recorded, a second measurement will be taken. If more than one temperature is taken on the same day, the highest temperature should be recorded. Fever will be defined as a measured temperature $\geq 100.4^{\circ}\text{F}$ (38°C). Participants will be queried during Visits 1a and 2a on solicited injection site adverse events, which will be classified as mild, moderate, or severe as described in **Table 4**. Participants will also be queried during Visits 1a and 2a on common post-injection systemic symptoms as described in **Table 5**.

Unsolicited adverse events (AEs) will be collected and reported for the 7 days following each vaccine. Any reports of new rash within 7 days after each dose will prompt a call from the study team to ascertain severity and the likelihood of an allergic reaction. Concomitant medication use, and concomitant vaccinations will be assessed through 29 days after dose 2 or a booster dose. Serious adverse events (SAEs), adverse events of special interest (AESIs) and unscheduled medical care for COVID-19 illness will be assessed at 29 days after dose 2 of COVID-19 vaccine or a booster dose and through the end of the study (181 days after dose 2).

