Unsolicited adverse events, AESIs and SAEs will be graded as described in **Table 6**. Participants who report severe solicited adverse events or express any concern about symptoms/unsolicited events will be encouraged to follow up with their primary care provider. Study staff will assist with coordination of referral appointments as necessary. Parent/LAR will be asked to agree to the release of information to obtain and review medical records for any unscheduled medical appointments, including clinic visits and telehealth visits, through 29 days after the second dose. Frequency and occurrence of serious AEs (SAEs), AESIs and unscheduled medical care for COVID-19 illness will be assessed through 181 days after dose 2 or a booster dose.

Table 4: Injection-site Reactogenicity			
Symptom	Mild (Grade 1)	Moderate (Grade 2)	Severe (Grade 3)
Pain	Does not interfere with activity	Interferes with activity	Prevents daily activity
Tenderness	Does not interfere with activity	Interferes with activity	Prevents daily activity
Underarm or groin swelling on same side as vaccine	Does not interfere with activity	Interferes with activity	Prevents daily activity
Swelling	5-11 years: 5-20 mm	5-11 years: 21-70 mm	5-11 years: >70 mm
	12 years >: 20-50 mm	12 years >: 51 - 100 mm	12 years: >100 mm
Redness	5-11 years: 5-20 mm	5-11 years: 21-70 mm	5-11 years: >70 mm
	12 years >: 20-50 mm	12 years >: 51 - 100 mm	12 years: >100 mm

Table 5: Systemic Reactogenicity			
Systemic	Mild (Grade 1)	Moderate (Grade 2)	Severe (Grade 3)
Fever (°C)	≥ 38.0 – 38.4 ≥ 100.4 - < 101.1° F	>38.4 – 38.9 ≥ 101.1 - < 102° F	> 38.9° C ≥ 102° F

Table 5: Systemic Reactogenicity			
Feverishness	Does not interfere with activity	Some interference with activity	Prevents daily routine activity
Chills	Does not interfere with activity	Some interference with activity	Prevents daily routine activity
Headache	Does not interfere with activity	Some interference with activity	Prevents daily routine activity
Fatigue	Does not interfere with activity	Some interference with activity	Prevents daily routine activity
Muscle Pain	Does not interfere with activity	Some interference with activity	Prevents daily routine activity
Joint Pain	Does not interfere with activity	Some interference with activity	Prevents daily routine activity
Vomiting	Does not interfere with activity	Some interference with activity	Prevents daily routine activity

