Study site investigators will assess relatedness to COVID-19 vaccine or study procedures (related, possibly related, unlikely related, or not related) for SAEs and AESIs. Solicited symptoms in **Tables 4 and 5** will all be considered to be related to COVID-19 vaccine and causality assessment will not be done for these events. The study investigators will use their clinical judgement to make causality assessments and may consult the Safety Review Panel or CISA Project for assistance with causality determinations. The final causality assessment decision is the responsibility of the site PI where the subject was enrolled.

Reporting Adverse Events

SAEs and unanticipated problems will be reported to the CDC and all participating IRBs according to institutional requirements. Vaccination is not a study procedure.

Adverse events that occur in a recipient following COVID-19 vaccination should be reported to CDC's Vaccine Adverse Event Reporting System (VAERS). Vaccination providers are required by the Food and Drug Administration to report the following that occur after COVID-19 vaccination under Emergency Use Authorization:

- Vaccine administration errors
- Serious adverse events
- Cases of Multisystem Inflammatory Syndrome
- Cases of COVID-19 that result in hospitalization or death

Reporting is encouraged for any other clinically significant adverse event even if it is uncertain whether the vaccine caused the event. Information on how to submit a report to VAERS is available at <https://vaers.hhs.gov> or by calling [name].

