7.2.3 Secondary Objective

Secondary Objective - To assess the safety of simultaneous administration of COVID-19 vaccine with other routinely recommended vaccines among children and adolescent participants.

1) Tables will be produced that summarize each solicited local and systemic reactogenicity event by maximum classification (none, mild, moderate, and severe), as well as by moderate or severe through days 1-7 following COVID-19 vaccination for dose 1 and dose 2 or a booster dose. These tables will have the number and percentage for each classification and will be broken down by concomitant childhood vaccine status (yes/no) by each site and across all sites. (SOM 1, SOM 2 and SOM 3)

2) Tables will be produced that summarize each unsolicited adverse event by maximum classification (none, mild, moderate, and severe), as well as by moderate or severe through days 1-7 following COVID-19 vaccination for dose 1 and dose 2 or a booster dose. These tables will have the number and percentage for each classification and will be broken down by concomitant childhood vaccine status (yes/no) by each site and across all sites. (SOM 4)

3) Tables will be produced that summarize participants experiencing at least one serious adverse event or one AESI through the 29 days after dose 2 or a booster dose. This table will have the number and percentage for each outcome and will be broken down by concomitant childhood vaccine status (yes/no). (SOM5 and SOM6)

The proportions by concomitant vaccine status (yes/no) for secondary outcomes 1 to 6 will be descriptively assessed using an exact Mantel-Haenszel statistic calculated using the Proc Logistic command in SAS at the two-sided alpha 0.05 level. Further details will

be described in the statistical analysis plan. The analysis for exploratory objectives will be described in the statistical analysis plan.

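### The solicited local items do not say which injection site they refer to, so other vaccines' injection sites could raise local reaction rates in co-vaccinated children

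*Combined protocol and SAP*

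**What the plan says.** - **Collection.** Section 5.5: "Participants will be queried during Visits 1a and 2a on solicited injection site adverse events". No injection is named.
- **Definition.** Table 4 lists pain, tenderness, swelling and redness with no location. Its one cue to side is "Underarm or groin swelling on same side as vaccine", which does not say which vaccine.
- **Attribution.** The causality paragraph of Section 5.5 covers every item in both reactogenicity tables: these "will all be considered to be related to COVID-19 vaccine and causality assessment will not be done for these events".
- **Number of sites.** Section 1 reports guidance that "if multiple vaccines are administered at a single visit, each should be administered at a different injection site".
- **Comparison.** The secondary outcome measure in Section 2 sets children receiving "other routinely recommended vaccines simultaneously with each dose COVID-19 vaccine versus those receiving COVID-19 vaccine alone". Section 7.2.3 tabulates each local event by the participant's maximum grade, "broken down by concomitant childhood vaccine status (yes/no) by each site and across all sites" (site here means study site). The proportions are "descriptively assessed using an exact Mantel-Haenszel statistic calculated using the Proc Logistic command in SAS at the two-sided alpha 0.05 level".
- **Location data.** Section 5.3 records where each vaccine was given. No stated field links a reaction to that location.

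**The concern.** Following the guidance quoted in the Background, a child who receives another vaccine with the COVID-19 dose has at least two injection sites, and a child in the comparison group has one. If the diary item covers any injection site, the maximum grade is taken over more sites in one group than in the other. The co-vaccinated proportion is then pushed upward even when the COVID-19 site reacts exactly as it would have done alone.

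This bears on the study's only secondary objective, which addresses a gap named in the Background: sparse data on reactogenicity under co-administration. It would also raise the pooled primary local rates a little. A statistical analysis plan cannot repair it afterwards if the diary never recorded where the reaction was.

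The relatedness rule is a separate problem of labelling. It would label a reaction at another vaccine's site as related to COVID-19 vaccine. It does not change any tabulated proportion, because the tables in Sections 7.2.2 and 7.2.3 count solicited events whatever their relatedness.

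**Working it through.** The plan gives no figure to reproduce: Section 7.1 has no power or sample size calculation, and no Grade 2-3 local rate or co-vaccinated share is stated.

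**Direction.** Let p be the probability of an event at the COVID-19 site and q at another site. An any-site item records an event with probability between max(p, q) and min(1, p + q), and 1 − (1 − p)(1 − q) if the sites are independent. None of these is below p.

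**Inputs.**
- From the documents: N = 320 (Section 4.3); two-sided 0.05 (Section 7.2.3); any pain 86% after dose 1 in ages 12-15 (Section 1).
- Assumed: Grade 2-3 local rate 15% at each site; q = 30% for any pain at the other site; 30% Grade 2-3 systemic rate, independent of local events; co-vaccinated groups of 32, 64 or 80.
- Test: unstratified Fisher exact, by full enumeration, as a stand-in for the exact Mantel-Haenszel test, whose strata the protocol does not state.

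**Grade 2-3 local events, no change at the COVID-19 site.**
- Independent sites: 1 − 0.85² = 27.75% against 15%.
- Correlated sites: the extra risk is assumed to shrink to 6 points, giving 21% against 15%.

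| Co-vaccinated vs alone | 27.75% vs 15% | 21% vs 15% | 15% vs 15% |
|---|---|---|---|
| 80 vs 240 | 67% | 22% | 4.0% |
| 32 vs 288 | 40% | 14% | 3.6% |

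Entries are the chance of p ≤ 0.05. The last column is the result if the items are tied to the COVID-19 site.

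**Grade 2-3 local or systemic combined (80 vs 240).**
- Co-vaccinated, independent sites: 1 − 0.7225 × 0.70 = 49.4%.
- Co-vaccinated, correlated sites: 1 − 0.79 × 0.70 = 44.7%.
- COVID-19 vaccine alone: 1 − 0.85 × 0.70 = 40.5%.
- Rejection: 26% (independent) and 9% (correlated).

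**Any pain (64 vs 256).** 1 − 0.14 × 0.70 = 90.2% against 86%; rejection about 10%. With q = 10% it is 4%, and with q = 50% it is 27%. The high base rate leaves little room for an excess.

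**Pooled primary local rate.** With 25% co-vaccinated (80 of 320), the Grade 2-3 rate rises by 0.25 × 12.75 = 3.2 points (independent) or 0.25 × 6 = 1.5 points (correlated). With 10% (32 of 320) it rises by 1.3 or 0.6 points.

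**The case against.** **The text leans towards the COVID-19 site.** The protocol summary ties injection-site data to each COVID-19 dose. Table 4 speaks of one vaccine in the singular. The perception items in Tables 7 and 8 contrast the vaccine site with other vaccines received. Calling all Table 4 events COVID-19-vaccine-related is natural if they are COVID-19-site events. Families are trained on a memory aid that the documents do not contain, and the detailed analysis plan is deferred. This stands in part. A reader might infer that the protocol counts reactions at every site, so that co-vaccinated children must show more local events by construction. The documents do not support that: they are silent, and the restriction is plausible but unstated.

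**Total burden is a legitimate target.** The objective is the safety of simultaneous administration, and a second sore arm is then a real consequence of the visit. This stands. The criticism is that the plan does not say which target it means. Recording by site serves both.

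**The relatedness rule does not drive the comparison, and review is not barred.** Both stand. Only causality assessment is omitted; for web-based diaries, staff still telephone about missing values, hives and Grade 3 events.

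**The test is descriptive and the groups are not randomised.** True, but a 0.05 level is set. Confounding may mask or add to the shift, so the upward direction holds in expectation, other things being equal.

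**POM 2 and 3 may be composites.** If so, systemic events dilute the excess, as the combined calculation shows. Section 7.2.3 still tabulates each local event separately.

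**Conclusion.** The concern holds as a gap in the outcome definition. Unless the memory aid ties the items to the COVID-19 site, local rates in co-vaccinated children are raised in expectation with no change at that site, and pooled primary local rates are raised slightly.

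The direction follows from the definition; the size does not. Depending on the assumptions, the exact-test rejection rate with no change at the COVID-19 site is about 14% to 67% for Grade 2-3 local events, about 26% for the composite with independent sites, and about 10% for any pain. A reader might take 67% as the false-positive rate of the planned test. It is only the top of the range shown, and it rests on an assumed 15% rate, independent sites and an 80 vs 240 split. If total local burden is the intended target, the excess is a real effect of the visit and not an artefact.

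The change is cheap and worth making before data are collected.

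**What to change.** In Table 4, Section 5.5 and the memory aid, record solicited local reactions by injection site. Identify the COVID-19 site once the vaccine has been given, because the memory aid may be dispensed up to 3 days beforehand. Record limb and, where two vaccines share a limb, position; different sites need not be different limbs.

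Then state in the analysis plan that:
- COVID-19-site events form the local part of POM 1-3 and the like-for-like secondary comparison;
- any-site local burden is reported separately;
- the automatic-relatedness rule, for local events, covers the COVID-19 site only.

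The cost is one added diary item, wording changes in Table 4 and Section 5.5, and a short addition to the analysis plan. Vaccine location is already recorded under Section 5.3. The downside is a slightly longer diary for co-vaccinated children.

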- Obtain parental permission by written informed consent and a release of medical record information, based on site IRB requirements
- Obtain assent from child, based on site IRB requirements
- Review and confirm study eligibility
- Obtain information on preferred method of contact for follow-up (telephone or email, or text reminder reminder)
- Obtain demographic data & COVID-19 vaccine history
- Obtain history of vaccines within 2 weeks of enrollment
- Obtain medical history, including COVID-19 disease history
- Obtain concomitant medication and vaccine use
- For children at participating sites, obtain optional blood sample within 3 days before or after vaccination for serologic analysis
- Dispense thermometer, ruler (in order to standardize measurements) and memory aid. Review instructions for use of thermometer, ruler, and memory aid completion. Preference will be to complete the memory aid electronically, with paper as a back-

up.

- Confirm anticipated date of COVID vaccine, if not already occurred
- Confirm date of next scheduled study visit

Visit 1a, Days 1-7 after dose 1 (Phone Visit)

- Subjects/parent/LAR will complete their memory aid via paper or electronic entry at approximately the same time each day for days 1-7, study staff will review subject-entered data within the database or by phone contact
- For participants using REDCap web-based system:
 - Study staff will send daily reminders to fill out the symptom diary
 - Record clinical data related to COVID diagnoses
 - Study staff will review REDCap system to confirm data capture and assess for any AE, AESIs, or SAEs on day 3 and 7 after vaccine
 - If any missing values, reported hives, or Grade 3 events occurred, the study staff will use phone contact to gather more information
 - The first parental and adolescent (if applicable) survey will be administered on day 7 after vaccine
 - Study staff will verify date of next COVID-19 vaccine and remind subjects to complete memory aid with next dose
- For participants using paper diary:
 - Study staff will call participants on day 3 after vaccine as a reminder to fill out the symptom diary
 - The first parent and adolescent (if applicable) survey will be administered on day 7
 - Study staff will call participants on day 7 (+ 3 days)
 - Record symptom diary
 - Record COVID-19 diagnoses
 - Record first parental and adolescent (if applicable) survey
 - Verify date of next COVID-19 vaccine and remind subjects to complete memory aid with next dose

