An adverse event (AE) is any untoward medical occurrence in a patient or clinical investigation subject administered a pharmaceutical product and which does not necessarily have to have a causal relationship with this treatment. Participants (or their parents) will be encouraged to report any significant unsolicited adverse events in an open-ended question format, e.g. "How are you (or your child) doing? Are you (or your child) having any medical or clinical problems? If so, please tell me about them."

An adverse event of special interest (AESI) includes the following:

- Allergic type reactions (including anaphylaxis, hives, or facial and limb swelling occurring within 7 days of a vaccination visit)
- Myocarditis or pericarditis occurring during the study period
- Multisystem inflammatory syndrome in children (MIS-C) during the study period

A serious adverse event (SAE) is defined as an AE that meets one of the following conditions:

- Results in death during the period of protocol-defined surveillance
- Is life-threatening (defined as immediate risk of death at the time of the event)
- Requires inpatient hospitalization or prolonged hospitalization during the period of protocol-defined surveillance (other than routine hospital admission for an elective medical procedure or surgery)
- Results in congenital anomaly or birth defect
- Results in a persistent or significant disability/incapacity
- Any other important medical event that may not result in death, be life threatening, or require hospitalization, may be considered an SAE when, based upon appropriate medical judgment, the event may jeopardize the subject and may require medical or surgical intervention to prevent one of the outcomes listed above. Examples of such medical events include allergic bronchospasm requiring intensive treatment in an emergency room or at home, blood dyscrasias or convulsions that do not result in inpatient hospitalization, or the development of drug dependency or drug abuse.

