Diarrhea	Does not interfere with activity	Some interference with activity	Prevents daily routine activity
Nausea	Does not interfere with activity	Some interference with activity	Prevents daily routine activity
Facial or lip swelling	Does not interfere with activity	Some interference with activity	Prevents daily routine activity

Table 6: Grading for Unsolicited Adverse Events, AESIs and SAEs			
Mild (Grade 1)	Moderate (Grade 2)	Severe (Grade 3)	
Does not interfere with activity	Some interference with activity	Prevents daily routine activity	

In this study, COVID-19 vaccination is not a study procedure. COVID-19 vaccine administration will be given per standard of care to children and adolescents receiving vaccine under an EUA by the Food and Drug Administration. Published studies in children and adolescents found no vaccine-related serious adverse events in children or adolescents receiving BNT162b2 (3-5). Lymphadenopathy was identified as an adverse event occurring more frequently in BNT162b2 vs. placebo groups during clinical trials (11). Post-authorization vaccine safety data have identified two safety concerns that rarely can occur after vaccination: severe allergic reactions, including anaphylaxis, and myocarditis and pericarditis (11). Therefore, we do not anticipate any significant issue with serious adverse events (SAEs). Nevertheless, we will monitor study participants for SAEs during the protocol-defined surveillance period of 6 months after second dose or a booster dose. SAEs will be reported to the CDC and all participating IRBs according to institutional requirements.

Perceptions of COVID-19 vaccine

At Day 7 (+3) following each of the vaccination visits we will assess adolescent (ages 12 to < 16) and parent/LAR perceptions of the COVID-19 vaccine recommendations and experience with receipt of the vaccine. Questions are provided in **Tables 7 and 8** below. We will use a Likert scale (strongly agree, agree, neither, disagree, strongly disagree) to assess response to the questions about concerns regarding COVID-19 vaccine safety. As noted, adolescent and parent perceptions regarding vaccine receipt will be assessed at the reactogenicity assessment visits after each vaccine.

Table 7 Parental /LAR Perceptions of COVID-19 Vaccine Recommendations and Receipt

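### Primary outcome POM 5 may be under-ascertained or inconsistently classified for mild allergic-type AESIs, because hives, rash and limb swelling are not solicited and follow-up of facial swelling depends on diary mode

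*Combined protocol and SAP*

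**What the plan says.** Section 2 defines POM 5 as "Proportion of participants with an adverse event of special interest through 29 days after dose 2" of COVID-19 vaccine or a booster. Section 5.5 gives the AESI components. The allergic one is "Allergic type reactions (including anaphylaxis, hives, or facial and limb swelling occurring within 7 days of a vaccination visit"; the others are myocarditis or pericarditis, and MIS-C.

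Section 5.5 also says that participants are queried at Visits 1a and 2a on the symptoms of Table 4 (injection site) and Table 5 (systemic). Table 4 covers pain, tenderness, swelling, redness and "Underarm or groin swelling on same side as vaccine". Table 5 covers fever and feverishness, general and gastrointestinal symptoms, and "Facial or lip swelling", the last graded 1 to 3 by interference with activity.

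For web-diary users, Section 5.1 (Visit 1a, with near-identical text at Visit 2a and in the booster schedule) says: "If any missing values, reported hives, or Grade 3 events occurred, the study staff will use phone contact to gather more information". Section 5.5 adds a call after any reported new rash within 7 days of a dose. Paper-diary users are all telephoned at Day 7 (+3).

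Other health problems are gathered as follows: "Participants (or their parents) will be encouraged to report any significant unsolicited adverse events in an open-ended question format".

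The causality text at the end of Section 5.5 treats every Table 4 and Table 5 symptom as vaccine-related, without individual assessment, but requires the site investigator to assess relatedness for AESIs.

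**The concern.** The call rules rest on reports of hives and rash, yet neither appears among the listed symptoms that families are asked about. Limb swelling, also named in the AESI definition, is solicited only as injection-site or underarm/groin swelling. Facial swelling is the reverse case. It is asked about daily and fits the AESI wording at any grade, but in a complete web diary only Grade 3 leads to a conversation.

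POM 5 is a primary outcome, and allergic reaction is one of the two post-authorization safety concerns the protocol itself names: "severe allergic reactions, including anaphylaxis, and myocarditis and pericarditis". If mild events are picked up differently by diary mode, or counted as AESIs at one site and only as reactogenicity at another, the proportion partly describes the collection method. The same events feed the by-group displays for concomitant vaccination (the secondary outcome) and baseline serostatus (EOM 2).

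**Working it through.** The plan gives no AESI rate, no ascertainment sensitivity and no sample size calculation (Section 7.1), so there is no figure to reproduce. The check sets the collection rules side by side.

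**Step 1. Each component against the rules for Days 1-7**

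| Component | In Tables 4/5? | Phone contact, complete web diary | Phone contact, paper diary |
|---|---|---|---|
| Hives | No | Yes, if reported | Everyone, Day 7 (+3) |
| New rash | No | Yes, if reported (Section 5.5) | Everyone, Day 7 (+3); also if reported |
| Limb swelling beyond injection site and underarm/groin | No | Only if reported and Grade 3 | Everyone, Day 7 (+3) |
| Facial or lip swelling, Grade 1-2 | Yes | No | Everyone, Day 7 (+3) |
| Facial or lip swelling, Grade 3 | Yes | Yes | Everyone, Day 7 (+3) |

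Electronic completion is the stated preference (Section 5.1), so the web column is likely to apply to most participants.

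**Step 2. Time to the next AESI contact for a web user who is not phoned**

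After dose 1, the next contact is Visit 2, at dose 2 (+3 days). After dose 2 or a booster, it is the visit with window Days 29-35. An event on Days 1-7 that was not entered must then be recalled after

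- shortest: 29 − 7 = 22 days
- longest: 35 − 1 = 34 days.

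**Step 3. What the other routes can recover**

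- Staff review of web entries for AESIs on Days 3 and 7 sees what was entered. It will see Grade 1-2 facial swelling, but not hives that nobody recorded.
- The diary also takes unsolicited events, but the inquiry described for them is open-ended, stresses significant problems, and gives no symptom prompts.
- The Day 29 visit solicits AESIs directly, at the recall interval above. The wording of that inquiry is not given.
- Medical record review (Section 5.3) finds events that reached care.

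A mild event that is not entered and never reaches care depends on recall at Day 29.

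**Step 4. Classification of facial swelling**

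As a Table 5 symptom it counts in the reactogenicity outcomes, is presumed related, and is exempt from causality assessment. As an AESI it counts in POM 5 and must be assessed. No rule says when the first becomes the second.

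**Step 5. Scale**

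With the planned 320 participants (60 + 100 + 70 + 90), one participant is 1/320 = 0.31 percentage points of POM 5. If none were observed, the exact two-sided 95% upper limit would be 1 − 0.025^(1/320) = 1.15%, and that reading assumes complete ascertainment. Neither figure estimates an under-count.

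**The case against.** The strongest reply is that the diary is not the POM 5 instrument. Table 3 lists AESIs as their own collection domain. The schedules have an AESI row at Visits 1a, 2, 2a, 3 and 4 (booster: 1a, 2 and 3). Staff review web entries for AESIs on Days 3 and 7 whatever the grade, AESIs are solicited at Day 29, and records are reviewed throughout. All of this stands. A reader might infer that POM 5 will be under-counted; the documents do not support that.

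The memory aid itself is not in the documents. Listing reported hives beside missing values and Grade 3 events is compatible with a hives field in the form. That also stands: the finding concerns Tables 4 and 5 and the call rules, and the form may already close part of the gap.

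A reader might also infer that facial swelling is missed. It is not: it is solicited daily and visible at staff review. The weakness is in follow-up and classification, and the missing call affects web users only.

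Finally, a reader might extend the point to chest symptoms, which are not in the tables either. The AESI is "Myocarditis or pericarditis occurring during the study period", a diagnosis sought by AESI inquiry and record review. The documents do not make a seven-day symptom item necessary to count it, so the point does not extend there.

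What the reply leaves untouched is the mild, unrecorded, untreated allergic-type event in a web user, the difference in contact between diary modes, and the missing rule for facial swelling.

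**Conclusion.** The point holds in limited form. For hives, rash, limb swelling and Grade 1-2 facial or lip swelling, POM 5 may be under-ascertained or inconsistently classified, and the handling differs between web and paper diaries. The first part assumes that the memory aid asks no more than Tables 4 and 5 list; the classification gap and the difference in calls do not depend on that assumption.

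The size of any under-count is unknown and cannot be derived, because the documents give neither an event rate nor a capture rate. A specific number of missed cases would rest wholly on invented inputs. The analysis is descriptive and several back-up routes exist, so this does not undermine the study. It is worth correcting because the outcome is primary and the change is small.

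**What to change.** 1. **Screening items.** Unless the memory aid already has them, add a separate AESI-screening block for Days 1-7 with two yes/no items: hives or new rash, and limb swelling away from the injection site. Keep it outside Tables 4 and 5 and outside POM 1-3. Putting the items in Table 5 would make them presumed-related symptoms exempt from causality assessment and would change the reactogenicity composites. If the form does contain such items, say so in Section 5.5. Alternatively, put a scripted AESI question to every participant at Day 7, whatever the diary mode.

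2. **Call trigger.** In the Visit 1a and 2a text, for both the primary series and the booster, keep missing values and Grade 3 events as triggers and extend the rest to: *any hives or rash, any limb swelling, and facial or lip swelling of any grade*.

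3. **Classification.** State when solicited facial or lip swelling counts as an AESI. Reconcile this with the causality text in Section 5.5, which at present both exempts the symptom and requires its assessment.

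The cost is two diary lines, one trigger sentence, one classification rule, and a few more calls for non-specific symptoms, made by staff who already review web entries on Days 3 and 7. The scripted-question alternative needs no diary change but adds a contact per dose for web users who would not otherwise be phoned.
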